**Hospital Security Program for Engaging Communities with Firearm
Safe Storage Devices and Interventions: Data Collection Aim 2**

Study Protocol

January, 2024

Outline

1. Abstract
2. Overall objectives
3. Aims
 - 3.1 Primary outcome
 - 3.2 Secondary outcomes
4. Background
5. Study design
 - 5.1 Design
 - 5.2 Study duration
 - 5.3 Target population
 - 5.4 Accrual
 - 5.5 Key inclusion criteria
 - 5.6 Key exclusion criteria
6. Subject recruitment
7. Subject compensation
8. Study procedures
 - 8.1 Consent
 - 8.2 Procedures
9. Analysis plan
10. Human research protection
 - 10.1 Data confidentiality
 - 10.2 Subject confidentiality
 - 10.3 Subject privacy
 - 10.4 Data disclosure
 - 10.5 Data safety and monitoring
 - 10.6 Risk/benefit
 - 10.6.1 Potential study risks
 - 10.6.2 Potential study benefits
 - 10.6.3 Risk/benefit assessment

1. Abstract

To prevent workplace violence, in November 2021, Penn Medicine implemented the Evolv weapons detection system in Pennsylvania Hospital (1,2). For individuals who self-disclose they are carrying a weapon, or who are identified with weapon during screening, security guards offer the individual the option to leave with their weapon, or to place it in a safe, at the hospital, for storage. Security guards return the weapon when the patient or visitor is ready to leave. Beginning in July 2022 our team piloted a program in which security guards offer a cable lock and safety brochure when the gun owner returns to retrieve their firearm at the conclusion of their visit. To date, 47% of patients and visitors who stored their firearm with security have taken a cable lock when offered, resulting in over 300 firearm safety locks and brochures distributed to firearm owners. The Aims of this study are to: (1) Elucidate barriers and facilitators to implementing a hospital security screening firearm safety program through interviews with hospital security staff; (2) Design and pilot test a method for collecting data on storage device use among patients and visitors who accept firearm safety materials; (3) Conduct a pilot of distributing lockboxes and compare acceptance and usage rates to cable locks.

This protocol is for Aim 2 of the study. The rationale for this aim is that traditional research methods for collecting data on firearm safe storage have not been optimized for use in a pragmatic setting to ensure acceptability and confidentiality. Our priority in firearm safety education and device distribution is to get the necessary information and supplies to those who need them. To achieve this, any data collection must be done in a low profile, confidential, and non-threatening way. This is particularly important not only because discussions of firearm ownership can be politically charged, but also because some community members may not be legally licensed to own or carry a firearm, and some may even be legally prohibited from doing so. The legal status of their ownership does not lessen their need for safety information and support—indeed, unlicensed firearm owners may have even fewer safety resources available for them. Our priority is therefore to reach as many individuals as possible while subjecting them to as little scrutiny as possible. Therefore, we aim to design a data collection approach that will prioritize preserving participant confidentiality. Our approach will be iterative pilot tests of data collection methods including embedding unique QR codes linked to surveys in firearm safety brochures and study poster signage. The hypothesis we are testing is if iterative pilot testing will reveal a feasible method that balances pragmatism and confidentiality.

The intended outcome of this study is development of critical evidence to facilitate the scaling of this program to our hospitals and launch a promising research program to study the acceptability, long term use, and cost-effectiveness of a scalable approach to promote safe firearm storage.

2. Overall objectives

Paralleling national trends during the Covid-19 pandemic, in 2021 in Philadelphia, there was a 600% increase in new firearm licenses, resulting in a large increase in new firearm owners (16). Effectively promoting secure storage of firearms among new and pre-existing owners could have a major impact on injury prevention, but existing educational and legislative means have had limited impact on promoting safe storage.

Firearm owners are open to talking about secure storage with healthcare providers, firearm experts, and law enforcement and security representatives (12–14,17–19). Firearm safety programs have shown greater success when they pair safety education with distribution of firearm safety devices (20,21). However, for reasons of expense and convenience, the most common device that programs distribute is a cable lock. Cable locks thread through the barrel or stock of a firearm. They require the weapon to be unloaded and they require a key to open them. Given that the number one reason for firearm ownership is fear of other people (22,23). Secure storage initiatives must be responsive to firearm owners' emphasis on

swift and easy access to their weapon in a time of emergency (6). Firearm owners rank speed and ease of use most highly when selecting storage devices and have preference for lockboxes over cable locks (5).

Building on success in reaching firearm owners in clinical and community settings, this innovative program addresses crucial gaps in firearm safety programming. First, we will expand upon a novel, successful program of firearm safety education and device distribution in the context of hospital security. Elucidating the barriers, facilitators, and opportunities in this space will allow us to scale our efforts throughout Penn Medicine and to many other health systems and settings around the country. Second, by adding a voluntary, anonymous initial survey linked via QR code within our educational materials and posted signage with the option to participate in a follow-up survey with link sent via text, we will have the opportunity to gather firearm owners' perspectives on storage and related issues to enable ongoing programmatic improvement. The study poster will test scalability and feasibility around distribution by asking individuals if and where they would like a firearm storage device shipped to them for convenience. Third, we will offer the most desirable locking device, biometric lockboxes, as an alternative to cable locks, along with firearm safety education. Providing these devices will amplify ongoing firearm safety efforts at Penn Medicine and in our partner communities.

3. Aims

3.1 Primary outcome

The primary outcome measure is survey response rate: whether an eligible visitor or patient completed the firearm storage survey after accepting firearm safety materials or after scanning the QR code on the study poster.

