3.3 Exploratory outcomes

To compare survey response rates between several different variations of survey distribution: web survey accessed via QR code posted in the entry hall; web survey accessed via QR code included on the safety brochure; follow-up survey link administered by text message.

4. Background

Firearm injury is the leading cause of death of children in the U.S. and Philadelphia (3). Our work shows unintentional injuries are the leading cause of nonfatal firearm injuries with rates disproportionately higher in Black communities (Figure 1). As in Philadelphia, forty percent of American adults live in a household with at least one firearm, and two thirds of these have at least one firearm that is unlocked (4–6). Secure storage of firearms can prevent youth suicide, unintentional injury, intimate partner homicide, theft, and violent crime (7–10). Education and legislation have had limited impact on promoting safe firearm storage (11–15).

[figure not shown]

Figure 1: Annual U.S. Firearm Injury Rates per 100,000 by Intent, Age, Race, and Ethnicity, 2019-20 (Kaufman...Delgado, under review)

Penn Medicine prohibits firearms within its buildings. In November 2021, Penn Medicine implemented the Evolv weapons detection system in entrances to Pennsylvania Hospital and its medical office buildings (2). In the first 5 months of the program, there were over 300,000 screening encounters and 408 firearms identified and stored by hospital security. In July 2022 our team piloted an innovative program in which security guards offer a firearm cable lock and safety brochure when the gun owner return to retrieve their firearm at the conclusion of their visit. To date, 47% of patients and visitors who stored their firearm with security have taken a cable lock when offered, resulting in over 300 firearm safety locks and brochures distributed to firearm owners.

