5.1 Design

Aim 2 of this research study is to design and pilot test a method for collecting data on storage device use among patients and visitors who accept firearm safety materials or are interested in receiving a firearm storage device shipped to their address. The study design is an iterative pilot test of survey data collection methods and determination of scalability and feasibility for distribution of firearm storage devices. The study population and sample will be (a) individuals who are patients or visitors to PAH who are screened

for a firearm, screen positive, and accept a firearm safety brochure and storage device OR (b) individuals interested in receiving a firearm storage device and self-scan the unique QR code on the study poster in the entry hall of PAH with minimal or no security supervisor engagement. A unique QR code linking directly to the initial survey will be embedded into the firearm safety brochure as well as the poster in the entry hall of PAH next to the distribution area. Individual group (a) will be informed by security that survey participation is optional, but that it is helpful for our efforts, and that participation will be compensated with a \$10 Amazon gift card for the initial survey and a \$20 Amazon gift card for completing the follow-up survey. Individual group (b) will not be actively engaged by security, and will self-enroll in the study by viewing the posted signage and completing the QR code linked survey. Individuals who decline the device will also be eligible for the initial survey via the poster QR code, but they will not be eligible for the follow-up survey.

The primary outcome measure is survey response rate: whether an eligible visitor or patient completed the firearm storage survey after accepting firearm safety materials or after scanning the QR code on the poster. This will be measured through Qualtrics survey completion rate and PAH Evolv security system foot traffic. We will use the survey completion rate as the numerator and the number of people scanning positive for a firearm as the denominator for this rate.

The secondary outcome measures are from initial and follow-up survey responses: (1) firearm storage behavior, (2) likelihood of using cable lock within the next week (extremely unlikely to extremely likely scale). These outcomes are directly tied to questions asked in both surveys.

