5.5 Key inclusion criteria

Individuals who are visitors or patients at Pennsylvania Hospital, are identified through the Evolv system as carrying a firearm, and who accept firearm safety materials OR any patient or visitor interested in receiving a firearm storage device who self-selects into the study by scanning the QR code on the study poster. For eligibility of the follow-up survey, participants must have responded yes to taking a cable lock

in the initial brochure survey or yes to receiving a firearm storage device shipped to their address from the poster survey.

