2. Have you used the firearm storage device from Penn Medicine to secure your firearm? [Yes/No]
3. Have you made any other changes in your firearm storage? [write in]

Iterative Analysis and Refinement of Data Collection Methods: We will assess response rates every (1) week and tabulate responses on the acceptability of data collection methods. We will iteratively refine data collection methods over the course of 6 months to achieve the highest possible response rate. The participant data collected will be their phone number and/or their address for individuals completed the survey via the study poster. No identifying information or demographics will be collected to uphold anonymity. Cell phone number will be used to distribute the gift card via the Nudge Unit’s Google Voice account and re-contact with invitation to participate in the follow-up survey. Their address will only be used to ship the firearm storage device to individuals who self-enrolled in the study via the study posters.

9. Analysis plan

The primary outcome is survey response rate. This will be monitored via Qualtrics by looking at response volume by week. These responses will be compared to security department reports on the number of firearms identified/stored to allow us to calculate the proportion of eligible individuals who responded per week. The secondary outcome measures are: (1) firearm storage behavior among a) locked safe/gun cabinet, b) trigger lock or cable lock, c) unsecured, d) other (write in), (2) likelihood of using cable lock within the next week (extremely unlikely to extremely likely scale).

10. Human research protection

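### The poster has no valid response-rate denominator: the eligible sets in 3.1 and 5.5 and the denominators in 5.1 and section 9 disagree, so the channel comparison in 3.3 sets side by side rates that are not comparable

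*Protocol*

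**What the plan says.** Section 3.1 makes the response rate the primary outcome and asks whether an eligible person "completed the firearm storage survey after accepting firearm safety materials or after scanning the QR code on the study poster".

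Section 5.5 admits people by two routes. Brochure participants "are identified through the Evolv system as carrying a firearm, and who accept firearm safety materials". Poster participants are "any patient or visitor interested in receiving a firearm storage device who self-selects into the study by scanning the QR code on the study poster"; no positive screen is required of them. Section 5.1 adds a further group: "Individuals who decline the device will also be eligible for the initial survey via the poster QR code".

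On measurement, section 5.1 says: "This will be measured through Qualtrics survey completion rate and PAH Evolv security system foot traffic". It then names the number of people who screen positive for a firearm as the denominator. Section 9 sets weekly Qualtrics responses against the security department's count of firearms identified or stored, in order to "calculate the proportion of eligible individuals who responded per week".

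Section 3.3 lists an exploratory outcome: "To compare survey response rates between several different variations of survey distribution: web survey accessed via QR code posted in the entry hall", against the brochure code and the texted follow-up link. It gives no denominator for any channel.

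**The concern.** A response rate needs a numerator drawn from its denominator, and two rates can be compared only if they start at the same stage. Neither condition is met for the poster. The brochure's eligible set includes people who took the brochure and never scanned it, whereas the poster's eligible set in 5.5 begins at the scan. The denominators written in 5.1 and section 9 are counts of firearm carriers or firearms, and poster participants need not be among them.

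Sections 5.4 and 8.2 use weekly response rates to refine the collection methods towards the highest possible rate. If the channel rates have different or invalid bases, a difference between them may reflect the choice of denominator and not how well the channel works.

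**Working it through.** The protocol gives no expected response rate, sample size or channel rate, so there is no stated figure to reproduce. The arithmetic below is illustrative.

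**Reading A: the eligible sets of 3.1 and 5.5 as denominators.** Let s be the probability of scanning and c the probability of completing once scanned, equal in both channels. The documents give neither.

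- Brochure rate, over accepters: s × c
- Poster rate, over scanners: c
- Ratio of poster to brochure: c / (s × c) = 1/s

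| s (assumed) | Brochure rate, c = 0.8 | Poster rate, c = 0.8 | Ratio |
|---|---|---|---|
| 0.05 | 4% | 80% | 20 |
| 0.20 | 16% | 80% | 5 |
| 0.50 | 40% | 80% | 2 |

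The ratio does not depend on c.

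**Reading B: the denominator of 5.1 or section 9.** Inputs from section 4 are 408 firearms identified and stored in the first 5 months, and 47% of those who stored a firearm taking a lock when offered. The 6-month active phase is from 5.2.

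- Positives in 6 months, if the rate is unchanged and one firearm is taken as one person: 408 / 5 × 6 = 489.6, about 490
- Accepters: 0.47 × 489.6 = 230.1, about 230
- Brochure completions, assuming 20% of accepters complete: 0.20 × 230.1 = 46.0
- Brochure rate over positives: 46.0 / 489.6 = 9.4%

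| Poster completions (assumed) | Poster / positives | Brochure / positives | Both channels pooled / positives |
|---|---|---|---|
| 10 | 2.0% | 9.4% | 11.4% |
| 50 | 10.2% | 9.4% | 19.6% |
| 230 | 47.0% | 9.4% | 56.4% |
| 600 | 122.5% | 9.4% | 131.9% |

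The poster is below the brochure with fewer than 46 completions and above it with more. It passes 100% beyond about 490. On a shared denominator the comparison is only one of completion counts. The pooled rate passes 100% once poster completions exceed 489.6 − 46.0 = 443.6.

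**Does either denominator contain the poster group?** Section 5.5 admits any interested patient or visitor. Section 4 reports 408 firearms in more than 300,000 screening encounters, at most 408 / 300,000 = 0.14%. The written denominator therefore covers a very small part of the traffic from which poster respondents can come. It also includes people who screened positive but accepted no materials, which lowers the brochure rate: 20% over accepters becomes 9.4% over positives.

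**The case against.** A reader might infer that the comparison favours the poster by construction, by the factor 1/P(scan). The documents do not support that as a general statement. Nowhere does the protocol divide by poster scanners. Section 5.1 names positive screens, and in section 9 the proportion of eligible responders is to be calculated from the firearms count. On those denominators a poster that almost everyone ignores shows a low rate (2.0% against 9.4% in the illustration). The inflation belongs to Reading A only.

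Nor does every poster participant become eligible only by scanning. Section 5.1 makes people who decline the device eligible through the poster code without stating that the scan confers eligibility, and those who screened positive are in the written denominator. For them the count is appropriate; for the rest of the poster group it is not.

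A reader might also infer that this comparison decides which channel is scaled up. The protocol describes weekly refinement and a general aim of scaling, but no text ties the choice of channel to this comparison.

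Finally, how to compute an exploratory rate is commonly left to the SAP, which is not at hand. That would answer silence on the point. It does not answer a protocol that states an eligible set and two denominators which do not match each other.

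**Conclusion.** The point holds in limited form. Entry to the eligible population starts at different stages for the two QR channels, and neither written denominator is the source population for poster participants, who need not screen positive. The comparison in 3.3 is therefore invalid whichever text is followed. If the eligible sets are used, the poster is inflated by 1/P(scan), 2 to 20 times for s from 0.50 to 0.05. If the written denominator is used, the poster rate has no valid meaning, can exceed 100%, and the direction of the distortion is not fixed.

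The values of s and c, the 20% completion, the numbers of poster completions and the six-month scaling are assumptions. The 47% comes from the programme begun in July 2022, while the 408 firearms are from the first five months after November 2021. The conclusion that the rates are not comparable depends on none of these. The same mismatch enters the primary rate wherever poster completions are counted in its numerator; the channel comparison itself is exploratory.

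**What to change.** Amend sections 3.3 and 9, and align 5.1 with them:

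1. Compare the two QR channels at the same stage, as completions per survey opened, using Qualtrics starts and completions for each code.
2. Report brochure completions per brochure handed out, and follow-up completions per text sent.
3. Report poster completions as weekly counts. Completions per Evolv entry may be added as a descriptive figure only: entries are encounters and not people, they include visitors without firearms, and they may include entrances away from the poster, since section 4 places Evolv at the medical office buildings as well.
4. State that a poster rate over scanners, or over positive screens, will not be compared with a brochure rate over accepters.

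The cost is protocol wording and a weekly tally of brochures handed out; the Qualtrics and Evolv counts come from sources the protocol already names. The price is that the poster yields no true response rate among firearm owners, and that completions per survey opened says nothing about how many people ignored either code.

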3.2 Secondary outcome

The secondary outcome measures are from initial and follow-up survey responses: (1) firearm storage behavior, (2) likelihood of using cable lock within the next week (extremely unlikely to extremely likely scale).

3.3 Exploratory outcomes

To compare survey response rates between several different variations of survey distribution: web survey accessed via QR code posted in the entry hall; web survey accessed via QR code included on the safety brochure; follow-up survey link administered by text message.

4. Background

Firearm injury is the leading cause of death of children in the U.S. and Philadelphia (3). Our work shows unintentional injuries are the leading cause of nonfatal firearm injuries with rates disproportionately higher in Black communities (Figure 1). As in Philadelphia, forty percent of American adults live in a household with at least one firearm, and two thirds of these have at least one firearm that is unlocked (4–6). Secure storage of firearms can prevent youth suicide, unintentional injury, intimate partner homicide, theft, and violent crime (7–10). Education and legislation have had limited impact on promoting safe firearm storage (11–15).

[figure not shown]

Figure 1: Annual U.S. Firearm Injury Rates per 100,000 by Intent, Age, Race, and Ethnicity, 2019-20 (Kaufman...Delgado, under review)

Penn Medicine prohibits firearms within its buildings. In November 2021, Penn Medicine implemented the Evolv weapons detection system in entrances to Pennsylvania Hospital and its medical office buildings (2). In the first 5 months of the program, there were over 300,000 screening encounters and 408 firearms identified and stored by hospital security. In July 2022 our team piloted an innovative program in which security guards offer a firearm cable lock and safety brochure when the gun owner return to retrieve their firearm at the conclusion of their visit. To date, 47% of patients and visitors who stored their firearm with security have taken a cable lock when offered, resulting in over 300 firearm safety locks and brochures distributed to firearm owners.

This program is fully supported by health system leadership (Co-Is [name], [name]) in the context of the larger goal of scaling weapons detection to all Penn Medicine hospitals in Philadelphia. However, contextual evidence is needed to optimize the design of the program for widespread implementation. And to measure its impact, novel methods are needed to assess long term firearm storage device use. Lastly, there are known tradeoffs in acceptability and costs of cable locks vs. Lockboxes. Our long-term research goals are to conduct randomized trials to: (1) quantify whether there is increased sustained safe storage of firearms with lockboxes to assess the incremental cost-effectiveness; and (2) test different behavioral engagement strategies to promote sustained use of safe storage devices.

5. Study design

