Lastly, as exploratory outcomes, we will compare survey response rates between several different variations of survey distribution: web survey accessed via QR code posted in the entry hall; web survey accessed via QR code included on the safety brochure; follow-up survey link administered by text message.

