8.2 Procedures

Study procedure. A unique QR code linking directly to the survey will be embedded into our firearm safety brochure and study poster available in the entry hall of PAH. Participants who scan positive for a firearm and are offered safety materials (inclusive of the brochure) will be informed that survey participation is optional, but that it is helpful to our efforts, and that participation will be compensated with a \$10 Amazon gift card for completing the initial survey and a \$20 Amazon gift card for completing the follow-up survey. Individuals who decline the device will also be eligible for the initial survey via the poster QR code. Gift cards will be distributed digitally via text in accordance with the participants consent to share their phone number. Only eligible participants will receive a text with a link to complete the optional follow-up survey.

Participants who self-select into the study via the study poster will be linked to the initial survey in Qualtrics with one re-worded question based on context. Individuals will receive \$10 Amazon gift card for completing the initial survey and a \$20 Amazon gift card for completing the follow-up survey. Only eligible participants will receive a text with a link to complete the optional follow-up survey.

Initial Survey via Brochure. Upon scanning the QR code on the brochure, an individual will be brought directly to the initial Qualtrics survey. The first question of the survey is a statement outlining that the individual's participation is voluntary and informed. The individual must select agree or disagree before proceeding with the survey. If the individual chooses to agree, they will then begin the initial survey. After completion of the survey, they will receive a text message with their Amazon giftcard information within 1-2 weeks. The text will read, "Hello, this is Penn Medicine. Thank you for participating in our survey. As an appreciation for your time, please see below for your gift card information: [INSERT GIFT CARD #]"

This initial survey will focus on the following elements. Survey language may be refined during the research process:

- 1.
2. To receive an Amazon gift card and participate in future follow-up surveys, please enter your phone number.
3. Most recent visit to Penn Medicine (mm/dd/yyyy)
4. Did you get a cable lock today?
 - a. Yes
 - b. No
5. [IF NO #3] What's the reason you didn't accept one?
 - a. Already have one
 - i. [LOGIC] How often do you use it?

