 - i. [LOGIC] Which of the following storage devices would you prefer?
 1. Lock box
 2. Trigger lock
 3. Gun safe
 4. Calmshell / "life jacket"
 5. Gun cabinet
 6. In-vehicle lock
 7. Other/key/PIN/biometric (please specify):
 - c. Don't want to share my address
 - i. [LOGIC] Please select which of the following you'd be open to:
 1. Returning to Penn Medicine to pick up a free cable lock
 2. Receiving a free cable lock locally
 3. Other (please specify)
5. [IF YES #3] What is the best US shipping address for you?
 - a. [Text box fields for street, apt, city, zip, name]
6. How do you usually store your firearm?
 - a. In a locked safe or gun cabinet
 - b. With a trigger lock or cable lock
 - c. Unlocked (not secured with a lock, in a locked container, or not stored in a locked cabinet)
 - d. Other (please specify)
7. Once you receive your cable lock, how likely are you to use it in the next week?
 - a. Extremely likely

- b. Somewhat likely
- c. Neither likely nor unlikely
- d. Somewhat unlikely
- e. Extremely unlikely

Follow-up Survey: Participants who complete the initial survey and who agree to provide contact information will be contacted via text message 1 month after enrollment for a follow-up survey that adds questions about if and how participants have changed their storage behavior. The text language will read:

“Hello, this is Penn Medicine. Thank you for completing our initial survey. If you’re interested in taking the follow-up survey, please click the survey link below: [INSERT LINK]”

Participants will receive the second Amazon gift card incentive 1-2 weeks after completion of this survey. “Hello, this is Penn Medicine. Thank you for participating in our survey. As an appreciation for your time, please see below for your gift card information: [INSERT GIFT CARD #]”

The follow-up survey questions are subject to be amended based on the principal investigators’ discretion. Eligible participants from the initial survey, those who answered yes to accepting a cable lock, will be asked the following questions to understand if their behavior changed:

1. Since you’ve visited Penn Medicine, how have you stored your firearm? [option selection]
 - a. Participants select [a] in a locked safe or gun cabinet, b) with a trigger lock or cable lock, c) unlocked (not secured with a lock, in a locked container, or not stored in a locked cabinet), d) other (please specify) with an open comment box]

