Lastly, as exploratory outcomes, we will compare survey response rates between several different variations of survey distribution: web survey accessed via QR code posted in the entry hall; web survey accessed via QR code included on the safety brochure; follow-up survey link administered by text message.

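### The 1-month text follow-up is listed as a third survey distribution route, but its rate is retention among people who already responded and cannot be compared with the QR routes

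*Protocol*

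**What the plan says.** Section 5.1 states the exploratory aim: "we will compare survey response rates between several different variations of survey distribution". Section 3.3 names three routes: the poster QR code in the entry hall, then "web survey accessed via QR code included on the safety brochure; follow-up survey link administered by text message". The Detailed Description for the registry repeats the list and again ends with "follow-up survey link administered by text message".

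Other sections fix who receives the text:

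- Section 8.2: "Participants who complete the initial survey and who agree to provide contact information will be contacted via text message 1 month after enrollment". The phone number is requested inside the initial survey.
- Section 5.5: "For eligibility of the follow-up survey, participants must have responded yes to taking a cable lock" in the brochure survey, or yes to a shipped device in the poster survey.
- Section 8.2: "Only eligible participants will receive a text with a link to complete the optional follow-up survey".
- Section 5.1: people who decline the device may take the initial survey through the poster but are not eligible for the follow-up.

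The text leads to a different questionnaire, a "follow-up survey that adds questions about if and how participants have changed their storage behavior" (8.2). Section 7 pays 10 dollars for the initial survey and 20 dollars for the follow-up.

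**The concern.** A comparison of distribution routes needs the routes to be alternative ways of delivering the same survey to people who have not yet answered it. The two QR codes meet that description. The text link does not: it is a second contact with people who have already answered once. Set beside the QR rates under a common label, its rate looks like evidence about text messaging as a channel. What it measures is how many earlier responders answer again.

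At stake is what the pilot can say about distribution methods. This is the only between-route comparison that the protocol names, in a study whose purpose is to find a workable way of collecting data.

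**Working it through.** **Step 1. The three routes side by side** (protocol 5.1, 5.5, 7, 8.2)

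| | Poster QR | Brochure QR | Text link |
|---|---|---|---|
| Opens | Initial survey, one question re-worded | Initial survey | Follow-up survey |
| Reaches | "any patient or visitor interested in receiving a firearm storage device who self-selects into the study", and device decliners | People who screen positive and accept materials | Initial-survey completers with a phone number who took or requested a device |
| Timing | From the visit | From the visit | 1 month after enrollment |
| Gift card | 10 dollars | 10 dollars | 20 dollars |
| Security | Not actively engaged | Guard mentions the survey | Not involved |

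Nothing in the protocol sends the initial survey by text, or sends a text to someone who has not responded. Every text recipient has already come through one of the two QR routes.

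**Step 2. What the text rate can show on each base.** The protocol states no response rates, so there is no figure to reproduce and all rates below are assumed. Take brochure recipients only, and let

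- r = initial response among people who accept materials,
- e = share of completers who are eligible and give a number,
- f = follow-up response among links sent.

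Over accepters, the brochure rate is r and the text rate is r × e × f, which cannot exceed r. Over links sent, the text rate is f. With e = 1:

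| r | f | Brochure, over accepters | Text, over accepters | Text, over links sent |
|---|---|---|---|---|
| 0.20 | 0.60 | 20% | 0.20 × 0.60 = 12% | 60% |
| 0.10 | 0.40 | 10% | 0.10 × 0.40 = 4% | 40% |
| 0.40 | 0.60 | 40% | 0.40 × 0.60 = 24% | 60% |
| 0.20 | 0.05 | 20% | 0.20 × 0.05 = 1% | 5% |

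With e = 0.80, the first row gives 0.20 × 0.80 × 0.60 = 9.6% over accepters. On the common base, text can at best tie with the brochure, and only if e = f = 1. On links sent, it ranks above the brochure exactly when f > r. Neither base isolates the effect of the channel.

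**Step 3. Selection alone.** Suppose route has no effect. A share p of people answer any survey with probability a and the rest with probability b; the two answers are independent within each group, and every completer is texted. Then

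initial rate = p·a + (1 − p)·b

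follow-up rate among completers = [p·a² + (1 − p)·b²] / initial rate

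- p = 0.1, a = 0.8, b = 0.02: initial 0.080 + 0.018 = 9.8%; follow-up (0.0640 + 0.00036)/0.098 = 65.7%; ratio 6.7.
- p = 0.2, a = 0.6, b = 0.05: initial 0.120 + 0.040 = 16.0%; follow-up (0.072 + 0.002)/0.160 = about 46%; ratio 2.9.
- p = 0.3, a = 0.5, b = 0.05: initial 0.150 + 0.035 = 18.5%; follow-up (0.0750 + 0.00175)/0.185 = 41.5%; ratio 2.2.

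A several-fold apparent advantage for text is thus compatible with no difference between routes, before the different questionnaire, timing and gift card are considered.

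**The case against.** The strongest reply is that this is a matter of labelling. The protocol openly calls the third item a follow-up link, and completion at each contact point is legitimate feasibility information in a pilot of data collection. No passage says that the study will judge whether text beats a QR code. The outcome is exploratory, every rate used above is assumed, and the ceiling on the common base is an algebraic identity that the plan never proposes to compute.

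Most of this stands, and it limits the point to a minor one. The follow-up rate is worth reporting. It does not rescue the comparison as written: the plan places that rate in a list of distribution variations to be compared, and no other section takes it out.

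A reader might go further and infer that the team will choose text as its method, because 5.4 commits it to refine methods towards the highest response rate. Section 5.4 does not mention this comparison, so the documents do not support that reading. Nor do they support the view that text is bound to look better: in the last row of the Step 2 table it is lower on both bases.

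The choice of denominator for the brochure response rate is a separate question and does not follow from this point.

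**Conclusion.** The point holds in a narrow form. As the protocol is written, the text follow-up rate is 1-month retention conditional on an earlier response, and it cannot be compared with the QR routes as a distribution method. This rests on the eligibility rules in 5.1, 5.5 and 8.2 and needs no assumed number; the 2.2- to 6.7-fold range only illustrates how far selection could mislead under assumed response probabilities.

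The consequence is minor. The outcome is exploratory and no decision rule is attached. The primary and secondary outcomes are unaffected, and a reader should not infer that the primary response rate is compromised by this. Nor should a reader infer that the two QR routes cannot be compared. Both deliver an initial survey, so a descriptive comparison is reasonable if its limits are stated: it is non-randomised, and the routes differ in security engagement and self-selection (5.1).

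**What to change.** In 3.3, 5.1 and the registry text:

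1. Remove the text follow-up from the comparison of distribution methods. Report it separately as 1-month follow-up completion, meaning follow-up surveys completed divided by links sent, split by brochure and poster origin.
2. Limit the between-route comparison to the two QR codes for the initial survey, on one quantity available for both, for example completed initial surveys per week over the same weeks. Do not set a brochure rate against a poster count: poster respondents need not have screened positive (5.5), so the firearm-positive count is not a denominator for them.
3. Describe that comparison as non-randomised, with routes that differ in security engagement and self-selection.

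The cost is wording, plus carrying the route of origin through to the follow-up record. Recruitment, initial-survey content and incentives do not change. The price is that the comparison covers two routes instead of three, and is of completion volume rather than response rate.
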